6.1.2. Relationship of Adverse Events to Study Drug

Treatment-emergent AEs will be summarized by SOC, PT, and relationship to study drug.

Treatment-related AEs will be presented in a data listing.

6.1.3. Severity of Adverse Event

The TEAEs will be summarized by SOC, PT, and severity.

6.1.4. Serious Adverse Events

An SAE is defined as any event that

- results in death
- is immediately life threatening
- requires inpatient hospitalization or prolongation of existing hospitalization
- results in persistent or significant disability/incapacity
- is a congenital anomaly/birth defect

Important medical events that may not result in death, be life threatening, or require hospitalization may be considered SAEs when, based upon appropriate medical judgment, they may jeopardize the participant or may require medical or surgical intervention to prevent one of the outcomes listed in this definition. Examples of such medical events include allergic bronchospasm requiring intensive treatment in an emergency room or at home, blood dyscrasias or convulsions that do not result in inpatient hospitalization, or the development of drug dependency or drug abuse.

Social hospitalization, defined as inadequate family support or care at the participant's primary residence resulting in participant hospitalization, will not be considered an SAE.

Serious TEAEs will be summarized by SOC and PT.

All SAEs will be presented in a data listing.

6.1.5. Adverse Events Leading to Study Drug Discontinuation

Treatment-emergent AEs leading to study drug discontinuation will be summarized by SOC and PT and will be presented in a data listing.

6.2. Clinical Laboratory Evaluations

Blood and urine samples that will be collected for clinical safety laboratory tests (chemistry, coagulation, hematology, urinalysis, serology, and pregnancy testing) are indicated in [Table 8-1](#).

Laboratory assessment analysis will be performed at a central laboratory, with the exception of urine pregnancy testing which will be done at local laboratories.

Hematology, coagulation, serum chemistry, and urinalysis will be performed at the timepoints identified in [Appendix 14.1](#), [Appendix 14.2](#), [Appendix 14.4](#) and [Appendix 14.5](#). Additionally, unscheduled testing may be done during the study if medically indicated.

Abnormal clinical laboratory values will be flagged as either high or low (or normal or abnormal) based on the reference ranges for each laboratory parameter. The investigator will determine whether any of the abnormally high or low results are clinically significant or not clinically significant. Any clinically significant results will be entered into the eCRF as AEs, however the attribution of clinical significance will not be available in the data.

Actual results and change from baseline values for hematology, coagulation, serum chemistry, and urinalysis tests will be summarized by visit using descriptive statistics.

Shift from baseline in hematology, coagulation, serum chemistry, and urinalysis tests results relative to the reference range will be summarized by visit using the frequency count and percentage of participants in each category.

Refer to Section 4 for the definition of baseline.

All laboratory test results will be presented in data listings.

Table 8-1 Laboratory Assessments

Chemistry	Coagulation	Hematology	Serology
Total bilirubin	PT	HbA1c	anti-HCV
Direct bilirubin	INR	Leukocytes	anti-HIV
Alkaline phosphatase	aPTT	Erythrocytes	HIV antigen
gammaGT		Hemoglobin	HBsAg
AST		Hematocrit	Total hepatitis B core antibody
ALT		Thrombocytes (platelets)	
LDH		MCV	
Creatine kinase		MCH	
Creatinine ^a		MCHC	
Urea			
Uric acid			
Cholesterol			
HDL			
LDL			
Triglycerides			
Total protein			
Albumin			
Glucose			
Bicarbonate			
Inorganic phosphate			
Sodium			
Potassium			
Calcium			
Chloride			
Magnesium			
Lipase			
Apolipoprotein B100			
	Urinalysis		Pregnancy Test
	Hemoglobin (blood urine)		Serum β-hCG or urine pregnancy test ^c
	Ketones		
	Glucose		
	Protein		
	Leukocyte esterase		
	Nitrite		
	pH		
	Specific gravity		
	Microscopic analysis ^d (sediment, erythrocytes, leukocytes, casts, crystals, epithelial cells, and bacteria)		

Abbreviations: ALT, alanine aminotransferase; ANC: absolute neutrophils count; aPTT, activated partial thromboplastin time; AST, aspartate aminotransferase; β -hCG, β -human chorionic gonadotropin; gammaGT, gamma glutamyl transferase; HBsAg, hepatitis B surface antigen; HCV, hepatitis C virus; HDL, high-density lipoprotein-cholesterol; HIV, human immunodeficiency virus; INR, international normalized ratio; LDH, lactate dehydrogenase; LDL, low-density lipoprotein-cholesterol; MCH, mean corpuscular haemoglobin; MCHC, mean corpuscular hemoglobin concentration; MCV, mean corpuscular volume; PT, prothrombin time.

^a Creatinine (and calculation of glomerular filtration rate).

^b ANC will be calculated at Screening only. Neutrophils will be assessed at all other time points.

^c All women of childbearing potential will have a serum pregnancy test at screening. Urine pregnancy tests will be performed at specified subsequent visits prior to study drug administration. If a urine pregnancy test is positive, it must be confirmed by a serum pregnancy test.

^d Microscopic examination of the sediment if blood, protein, leukocytes esterase, or nitrite are positive on the dipstick.

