4.3.1. Part 1 (Treatment Period)

4.3.1.1. Withdrawal from Study Drug (Part1)

A participant may be discontinued from study drug at any time if the participant or the investigator feels that it is not in the participant's best interest to continue. The following is a list of possible reasons for study drug discontinuation:

1. Participant is noncompliant with the protocol
2. Participant is lost to follow-up
3. Participant withdraws consent
4. Participant has a serious or intolerable AE that, in the investigator' opinion, requires withdrawal from the study drug
5. Serum aminotransferase levels (ALT or AST) $>3 \times$ ULN AND total bilirubin $>2 \times$ ULN without an alternative explanation
6. Anaphylaxis
7. Infusion-related or injection-related reaction despite adequate premedication for an initial occurrence of a moderate to severe infusion-related reaction ([Section 5.1.2](#)) or if the participant experiences any of the following events: mucosal tissue involvement, airway compromise, or symptomatic hypotension with systolic blood pressure <90 mm Hg measured in the supine position
8. Occurrence of an intercurrent illness that, in the investigator's opinion, will affect assessments of clinical status or safety to a significant degree
9. Use of a nonpermitted concomitant medication per [Section 4.1.2](#) (as appropriate)
10. Pregnancy
11. Discretion of the investigator

If a participant is withdrawn from study drug due to an AE or SAE, the participant will be followed up by the investigator until the abnormal parameter or symptom has resolved or stabilized (if applicable). The investigator has the responsibility for all decisions regarding participant safety. It is recommended that the investigator consult with the Medical Monitor prior to removing the participant from study drug for any reason except participant withdrawal of consent and in case of medical emergency. If a participant is discontinued because of an AE or SAE, the event will be followed up until it is resolved. Any participant may withdraw his or her consent at any time.

All participants who discontinue study drug prior to the completion of the Part 1 96-week treatment period should be encouraged to complete all remaining scheduled assessment visits through the Part 1 treatment period (Week 97). Study staff will follow-up to aid in this goal.

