6.5.9. Laboratory Assessments

Blood and urine samples that will be collected for clinical safety laboratory tests (chemistry, coagulation, hematology, urinalysis, serology, and pregnancy testing) are indicated in [Table 3](#).

For any laboratory test value outside the reference range that the investigator considers clinically significant, the investigator will follow the instructions in [Section 7.3](#).

Laboratory assessment analysis will be performed at a central laboratory, with the exception of urine pregnancy testing or medically indicated emergency laboratory tests which will be done at local laboratories.

Table 3: Laboratory Assessments

Chemistry	Coagulation	Hematology	Serology
Total bilirubin	PT	HbA1c	anti-HCV
Direct bilirubin	INR	Leukocytes	anti-HIV
Alkaline phosphatase	aPTT	Erythrocytes	HIV antigen
gammaGT		Hemoglobin	HBsAg
AST		Hematocrit	Total hepatitis B core antibody
ALT		Thrombocytes (platelets)	
LDH		MCV	
Creatine kinase		MCH	
Creatinine ^a		MCHC	
Urea		Partial automated differentiation:	
Uric acid		Lymphocytes	
Cholesterol		Monocytes	
HDL		Eosinophils	
LDL		Basophils	
Triglycerides		Neutrophils ^b	
Total protein		ANC ^b	
Albumin			
Glucose			
Bicarbonate			
Inorganic phosphate			
Sodium			
Potassium			
Calcium			
Chloride			
Magnesium			
Lipase			
Apolipoprotein B100			
		Urinalysis	Pregnancy Test
		Hemoglobin (blood urine)	Serum β -hCG or urine pregnancy test ^c
		Ketones	
		Glucose	
		Protein	
		Leukocyte esterase	
		Nitrite	
		pH	
		Specific gravity	
		Microscopic analysis ^d (sediment, erythrocytes, leukocytes, casts, crystals, epithelial cells, and bacteria)	

Abbreviations: ALT, alanine aminotransferase; ANC, absolute neutrophil count; aPTT, activated partial thromboplastin time; AST, aspartate aminotransferase; β -hCG, β -human chorionic gonadotropin; gammaGT, gamma glutamyl transferase; HBsAg, hepatitis B surface antigen; HCV, hepatitis C virus; HDL, high-density lipoprotein-cholesterol; HIV, human immunodeficiency virus; INR, international normalized ratio; LDH, lactate dehydrogenase; LDL, low-density lipoprotein-cholesterol; MCH, mean corpuscular haemoglobin; MCHC, mean corpuscular hemoglobin concentration; MCV, mean corpuscular volume; PT, prothrombin time.

^a Creatinine (and calculation of glomerular filtration rate).

^b ANC will be calculated at Screening only. Neutrophils will be assessed at all other time points.

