8.1. Sample Size Estimations

Part 1 (Treatment Period)

The primary objective of Part 1 of the study is to assess the safety profile of repeat dosing of AL001 in asymptomatic and symptomatic participants. Descriptive statistics will be used to assess clinically significant associated findings (for example, study drug related AEs leading to study drug discontinuation or study drug-related SAEs). The Part 1 sample size of 40 participants was chosen based on feasibility; however, the probability of detecting at least 1 clinically significant associated finding will be explored. When the probability of a clinically significant associated finding for a single participant is 0.1%, 1%, 5%, and 10%, then with a sample size of 40 participants, the probability of detecting at least 1 clinically significant associated finding across all participants is 3.9%, 33.1%, 87.1% and 98.5% respectively.

Part 2 (Optional OLE)

It is estimated that up to 40 participants from Part 1 of the study will be eligible to continue with Part 2 of the study. Part 2 is optional for participants, and at the discretion of the investigator.

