8.4.2.8. Clinical Laboratory Analysis

Actual values and changes from baseline for clinical laboratory test results will be summarized at each time point using descriptive statistics. Shift tables will be generated for clinical laboratory test results.

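### SAP 6.2 assures unscheduled and local laboratory results no place in a table, plans no worst-value summary, and counts nobody against the protocol's ALT/AST-plus-bilirubin thresholds

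*SAP*

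**What the plan says.** SAP 6.2 plans two kinds of laboratory table. Actual results and changes from baseline in hematology, coagulation, chemistry and urinalysis "tests will be summarized by visit using descriptive statistics". For shifts the text is "Shift from baseline in hematology, coagulation, serum chemistry, and urinalysis tests results relative to the reference range will be summarized by visit", shown as counts and percentages per category. All results are also listed. Protocol 8.4.2.8 asks for values and changes at each time point and adds only that "Shift tables will be generated for clinical laboratory test results".

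On tests outside the schedule, SAP 6.2 says that "unscheduled testing may be done during the study if medically indicated". Protocol 6.5.9 has testing done centrally, "with the exception of urine pregnancy testing or medically indicated emergency laboratory tests which will be done at local laboratories". The matching sentence in SAP 6.2 names urine pregnancy tests as the only local exception.

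Protocol 4.3.1.1 item 5 (Part 1) and 4.4.1 item 12 (Part 2) give a hepatic criterion among the possible reasons for discontinuation. It begins "Serum aminotransferase levels (ALT or AST" and requires a value above 3 x ULN together with total bilirubin above 2 x ULN, with no other explanation.

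**The concern.** A by-visit table has a row for each planned visit. A result from a medically indicated extra draw has no row unless a rule assigns it one, and SAP 6.2 has no such rule. A low/normal/high shift also puts every value above the reference range in one category, whether it is 1.1 or 10 times the ULN, and it treats ALT, AST and bilirubin separately.

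The protocol names a joint liver elevation as important enough to be a possible reason for stopping study drug. A reader of the planned tables could not say how many participants reached it. In a single-arm study of about 40 people, one such participant is information that the safety report should show directly.

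**Working it through.** **1. The plan's own figure.** The only numerical design reasoning is in protocol 8.1 (repeated in SAP 2.1): with 40 participants and a per-participant risk of 0.1%, 1%, 5% or 10%, "the probability of detecting at least 1 clinically significant associated finding across all participants is 3.9%, 33.1%, 87.1% and 98.5% respectively". The formula is 1 - (1 - p)^40. It gives 0.0392, 0.3310, 0.8715 and 0.9852, so all four figures reproduce. The study is therefore justified by its chance of seeing at least one important finding, which makes single-participant laboratory events relevant.

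**2. Is there a rule for post-baseline unscheduled results?**
- SAP 2 applies analysis visit windows to COA and biomarker analyses. None is given for laboratory tests.
- SAP 2 lets repeated and unscheduled values before first dose serve as baseline. Nothing equivalent is said for values after first dose.
- Other safety sections are explicit. SAP 6.3 says which vital signs taken around the infusion are summarised. SAP 6.7 says that unscheduled ADA samples taken for infusion reactions are left out of the summary and listed. SAP 6.4 counts participants with at least one abnormal post-baseline ECG result against stated limits. SAP 6.2 has no counterpart to any of these.

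**3. Local emergency results.** The protocol allows them and SAP 6.2 omits them. SAP 12, which records changes to the planned analysis, does not mention the difference.

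**4. Can the joint threshold be read from the planned tables?** Suppose one participant is high for ALT and one is high for bilirubin at a visit. The two shift tables are the same whether this is one person or two, so the joint count could be 0 or 1. They are also the same at 1.1 x ULN and at 10 x ULN. The by-visit maximum (SAP 2 lists minimum and maximum) shows size for one analyte at one visit, but it does not link two analytes within a person.

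**5. Scheduled sampling.** Part 1 chemistry (protocol Tables 4 and 5; Week 97 is read from SAP Appendix 14.2) falls at Weeks 1, 5, 9, 13, 25, 37, 49, 61, 73, 85 and 97. That is 11 draws, with three gaps of 28 days and then seven of 84 days (for example Day 169 - Day 85 = 84). Dosing is every 28 days. Chemistry is also drawn at Part 1 EOT/EOS and Safety Follow-up.

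**6. Illustration, resting on assumptions that are not in the documents.** Take one abnormality per affected participant, with onset uniform within an 84-day gap and lasting D days. A scheduled draw overlaps it with probability min(1, D/84). The chance that scheduled draws show at least one case in 40 is 1 - (1 - p x min(1, D/84))^40.

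| D (days) | Overlap | p = 1% | p = 5% |
|---|---|---|---|
| 7 | 8% | 3.3% | 15.4% |
| 14 | 17% | 6.5% | 28.4% |
| 28 | 33% | 12.5% | 48.9% |
| 42 | 50% | 18.2% | 63.7% |
| 84 or more | 100% | 33.1% | 87.1% |

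A table using every result would restore the last row only if each case were sampled at an extra test. The illustration leaves out the EOT/EOS and follow-up draws. It shows why extra draws can matter, not how many results the plan would lose.

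**The case against.** The strongest reply is that the endpoint is change over time, that by-visit changes and shifts answer it and match protocol 8.4.2.8, and that other outputs cover the rest. Several parts of this stand.

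- A reader might infer that unscheduled and local results are barred from every table. The documents do not say so. SAP 6.2 is silent, whereas SAP 6.7 excludes certain unscheduled ADA samples in words.
- Clinically significant results become adverse events (SAP 6.2, protocol 7.3), are graded for severity (protocol 7.7) and appear in the AE tables. A participant withdrawn for a liver signal should also appear under AEs leading to discontinuation (SAP 6.1.5) or reasons for stopping study drug (SAP 3.1). It would be too strong to say that the tables as a whole would look clean.
- EOT/EOS assessments, which include chemistry, are due as soon as possible after the decision to stop, so a planned draw follows that decision.
- A reader might also infer that the worst values occur at unscheduled or local tests. Neither document says this.

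These routes do not close the gap. AE tables carry coded terms and severity but no laboratory values. Entry as an AE depends largely on the investigator's judgement, and SAP 6.2 states that the attribution of clinical significance will not be in the data. The hepatic criterion is one of several possible reasons for discontinuation, so a participant can meet it without being discontinued, and disposition counts cannot stand in for it. Listings show values but count nobody.

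**Conclusion.** The point holds as a gap in the output specification. SAP 6.2 has no rule for post-baseline unscheduled or local laboratory results, no worst-post-baseline summary, and no count of the ALT/AST and bilirubin thresholds that the protocol states for both parts. This rests on the text alone and needs no assumption.

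Its numerical size cannot be derived. The documents do not say how many unscheduled or local tests are expected, or whether local values enter the analysis database. The 84-day spacing is correct but is a sampling frequency, and the percentages under step 6 of the working depend on the assumed duration and onset. The change is worth making before the tables are produced: it concerns a primary safety endpoint, is cheap, and follows what the SAP already does for ECGs.

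**What to change.** Amend SAP 6.2 as follows.

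- (a) Add a shift table from baseline to the worst post-baseline value per participant. Use all scheduled and unscheduled results in the database, plus local results where both the value and its reference range are available.
- (b) Add a by-cohort count of participants with any post-baseline ALT or AST above 3 x ULN, any total bilirubin above 2 x ULN, and both in the same sample, with a listing of those participants. Requiring the same sample avoids joining elevations that were months apart. Label this as the laboratory component of the protocol criterion, because whether another explanation exists is a clinical judgement that a table cannot make. It uses the protocol's thresholds as they stand and adds no clinical rule.
- (c) Bring the local-laboratory sentence into line with protocol 6.5.9. While there, correct the cross-reference for baseline: SAP 6.2 points to Section 4, but the definition is in Section 2.

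The cost is SAP wording, two tables and one listing, with no new procedures for participants. The limit is local data. Protocol 11.3 has sites supply normal ranges for local laboratories used in the study, but it does not say that those ranges or the results are in the database. Where they are not, the tables should say that local results are excluded.

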6.3. Vital Signs and Weights Measurements

Vital sign measurements including systolic and diastolic BP, pulse rate, body temperature, respiratory rate, height, and weight will be collected at the timepoints identified in [Appendix 14.1](#), [Appendix 14.2](#), [Appendix 14.4](#) and [Appendix 14.5](#). Additional, unscheduled testing may be done during the study if medically indicated.

Supine systolic and diastolic BP, pulse, body temperature, and respiratory rate will be recorded after the participant has been resting for ≥ 5 minutes in the supine position.

Actual results and change from baseline values for vital signs will be summarized by visit and timepoint using descriptive statistics. Since the infusion is scheduled to last for approximately 60 minutes and Protocol section 5.5.4 allows for interruptions and rate reductions that would extend the infusion duration beyond 60 minutes, therefore; for summarization purposes all vital sign measurements collected during the infusion up to and including 60 minutes after the start of the infusion will be included. Vital sign measurements collected beyond 60 minutes after the start of the infusion and before the end of the infusion, in case that the infusion duration is beyond 60 minutes, will not be summarized. All vital sign measurements collected after the end of the infusion will be summarized. All vital signs data will be presented in a data listing.

Refer to Section 4 for the definition of baseline.

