5.1.2. Infusion-Related and Injection-Related Reactions

All participants will be monitored for infusion-related reactions or injection-related reactions during the infusion/injection and immediately afterwards for at least 60 minutes.

Injection-related reactions can be localized at the site of the injection or systemic and should be treated per institutional guidelines. If a participant experiences a mild infusion-related reaction,

the infusion should be halted. Once the reaction has resolved, the infusion rate will be resumed at half the most recently used rate (e.g., from 60 mL/hr [1.0 mL/min] to 30 mL/hr [0.5 mL/min]). The infusion should be stopped immediately for any participant who experiences a moderate to severe infusion-related reaction (e.g., fever or chills), and the participant should receive aggressive symptomatic treatment. The infusion should not be restarted before all symptoms have disappeared, and then it should be restarted at half of the initial rate. The infusion should not be resumed if there is a second occurrence or if the participant experiences any of the following events: mucosal tissue involvement, airway compromise, or symptomatic hypotension with systolic blood pressure <90 mm Hg measured in the supine position.

In addition, in the event of an infusion-related reaction, a sample of blood should be obtained for PK serum and ADA assessment of AL001, and testing should be performed for C-reactive protein, tryptase, and Interleukin 6 (IL-6). Further details regarding infusion-related reactions are provided in the IB.

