8.4.2.6. Vital Signs Analysis

Actual values and changes from baseline for vital signs and weight will be summarized at each time point using descriptive statistics.

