1.2. Study Design

This is a Phase 2, multicenter, open label study evaluating the safety, tolerability, PK, PD, and effect on COAs of AL001 administered intravenously (60 mg/kg, q4w) in asymptomatic and symptomatic carriers of loss-of-function GRN mutations causative of FTD and in symptomatic carriers of C9orf72 hexanucleotide repeat expansion mutations causative of FTD. This study has two parts: A phase 2 open-label treatment period (Part 1), followed by an optional open-label extension (OLE) period (Part 2).

Part 1 is a 96-week evaluation of the safety, tolerability, PK, PD, and clinical effect of AL001 administered intravenously (60 mg/kg, every 4 weeks [q4w]), for a total of 25 doses (96-week dosing period), in asymptomatic and symptomatic carriers of loss-of-function GRN mutations causative of FTD, and in symptomatic carriers of C9orf72 hexanucleotide repeat expansion mutations causative of FTD.

Part 2 is an optional OLE for eligible participants who have completed the 96-week Part 1 treatment period. The OLE period will evaluate the long-term safety and tolerability of AL001 administered at the same dose and regimen as Part 1 (60 mg/kg, q4w), for up to a total of 25 doses (96-week optional OLE period).

Figure 1-1 Overview of Study Schema

Abbreviations: COA, clinical outcome assessment; CSF, cerebrospinal fluid; *GRN*, granulin; IV, intravenous; MRI, magnetic resonance imaging; PD, pharmacodynamic; q4w, every 4 weeks.

2. General Statistical Considerations

All data collected from enrolled participants, excluding screen failures, will be presented in data listings. Data from participants excluded from an analysis set will be presented in the data listings but not included in the calculation of summary statistics for the corresponding analysis set.

Data from Part 1 and Part 2 will be combined and will not be analyzed separately.

For categorical variables, frequencies and percentages will be presented. Continuous variables will be summarized using descriptive statistics (number of participants, mean, standard deviation [SD], median, minimum, maximum, and 90% or 95% confidence interval [CI] where applicable). All summaries will be presented by the three cohorts [asymptomatic FTD-*GRN* (aFTD-GRN), symptomatic FTD-*GRN* (FTD-*GRN*), symptomatic FTD-*C9orf72* (FTD-*C9orf72*)] and All Participants.

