Baseline will be defined as the last non-missing assessment, including repeated and unscheduled measurements, prior to the start of first study drug administration.

Due to the high rate of participant attrition over the study duration and small FTD cohort sizes, time points beyond week 49 will not be included in the cohort level summary of the figures.

All CIs will be 2-sided and performed using a 5% significance level except for PK parameters for which, 90% CI and geometric mean will be used. All p-values will be presented to 3 decimal places and values less than 0.001 or greater than 0.999 will be presented as <0.001 and >0.999, respectively. As the objectives of the study are exploratory in nature no adjustments for multiplicity will be made.

No formal significance testing will be performed.

Analysis visit windows will be applied for COA and Biomarker analysis. A detailed explanation about the analysis visit windows will be described in the specific section of each analysis,

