d Vital signs will be recorded after the participant has been resting for at least 5 minutes in the supine position. On dosing days, vital signs will be recorded prior to infusion (pre-dose) and within 15 minutes after the end of infusion, and once at all other specified time points as indicated. Weight (kg) will be collected at the same visits that vital signs are taken.

e Triplicate 12-lead ECGs will be obtained after the participant has been in the supine position for ≥ 5 minutes. On specified dosing days ECG will be obtained prior to study drug administration and within 60 minutes after the end of infusion, and once at all other specified time points as indicated. Additional ECG monitoring must be performed during the treatment period if clinically indicated.

f Details on timing of vital signs, serum PK samples, triplicate ECGs, serum ADA samples, progranulin plasma samples, exploratory plasma PD biomarker samples, whole blood samples for WBC analysis, and exploratory whole blood PD biomarker samples are provided in protocol Table 6.

g Samples will be collected prior to study drug administration (if applicable).

h If the lumbar puncture is moved to a different visit, the coagulation panel will be moved to the visit immediately preceding the new lumbar puncture visit.

i Serology testing will include anti-HCV, anti-HIV, HIV antigen, HBsAg, and total hepatitis B core antibody.

j All women of childbearing potential will have a serum pregnancy test at screening. Urine pregnancy tests will be performed at specified subsequent visits. If a urine pregnancy test is positive, it must be confirmed by a serum pregnancy test.

k Blood serum samples will be collected for determination of ADA prior to study drug administration (if applicable). Additional ADA samples should be collected in participants with signs and symptoms of infusion-related reactions. A sample of blood should be obtained for PK serum and ADA assessment of AL001, and testing should be performed for C-reactive protein, tryptase, and Interleukin 6 (IL-6).

l Cerebrospinal fluid samples will be collected via lumbar puncture prior to study drug administration (if applicable). The timing of lumbar punctures may be adjusted as determined by Alector's review of exploratory PD biomarkers. GRN mutation carriers previously treated in Study AL001-1 may not be required to repeat the CSF assessment if it has been performed within 3 months prior to screening.

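### SAP 6.3 measures change in vital signs only from the pre-first-dose baseline and counts no cut-off, so the vital-sign tables give neither the spread of the acute change around an infusion nor the number of participants below 90 mm Hg systolic

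*SAP*

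**What the plan says.** - **Timing.** SAP Appendix 14.1, footnote d: "On dosing days, vital signs will be recorded prior to infusion (pre-dose) and within 15 minutes after the end of infusion". Protocol Tables 6 and 9 show a pre-dose and an end-of-infusion vital-sign row at every dosing visit, for up to 25 doses in each part.
- **Summary.** SAP 6.3: "Actual results and change from baseline values for vital signs will be summarized by visit and timepoint using descriptive statistics". Protocol 8.4.2.6 has the same plan: "Actual values and changes from baseline for vital signs and weight will be summarized at each time point using descriptive statistics".
- **Reference value.** SAP Section 2: "Baseline will be defined as the last non-missing assessment, including repeated and unscheduled measurements, prior to the start of first study drug administration". No per-visit reference is defined for vital signs.
- **Statistics shown.** SAP Section 2: "Continuous variables will be summarized using descriptive statistics (number of participants, mean, standard deviation [SD], median, minimum, maximum", plus a confidence interval where applicable.
- **Readings left out.** SAP 6.3 lists all vital signs but excludes one group from the summary when an infusion runs past 60 minutes: "Vital sign measurements collected beyond 60 minutes after the start of the infusion and before the end of the infusion".
- **The protocol's own figure.** Protocol 5.1.2 names "symptomatic hypotension with systolic blood pressure <90 mm Hg measured in the supine position" among the events after which an infusion is not resumed. The same event stands among the possible reasons for stopping in Protocol 4.3.1.1 (item 7) and 4.4.1 (item 14).
- **Contrast.** SAP 6.4 counts participants beyond ECG cut-offs, including heart rate below 60 and above 100 bpm. SAP 6.2 gives laboratory shift tables. SAP 6.3 has neither kind of table.

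**The concern.** Change in vital signs is one of the primary safety endpoints (Table 1 of both documents), and Protocol 1.3.1 names hypersensitivity-type reactions as the drug-class risk. The schedule yields a before-and-after pair at each infusion, yet no planned table uses the pair as a pair. After the first infusion, the change shown for an end-of-infusion reading combines whatever happened during that infusion with whatever has drifted since before the first dose. Nor does any table count participants at the one blood pressure figure that the protocol uses in its infusion rules. A reader of the study report who asks how far pressure moved around infusions, and in how many people it fell below that figure, would not find the answer in the vital-sign tables.

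**Working it through.** **1. The plan's own figure.** The only design calculation is the chance of at least one finding among 40 participants, 1 − (1 − p)^40. For p = 0.1%, 1%, 5% and 10% this gives 3.92%, 33.10%, 87.15% and 98.52%, matching the stated 3.9%, 33.1%, 87.1% and 98.5%. It does not involve vital signs. It does show that the plan describes its safety information as participants with at least one finding, which is the form that SAP 6.3 lacks.

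**2. Age of the reference value.** Up to 25 + 25 = 50 infusions are planned. The pre-first-dose value is normally the same-day value only at the first, which leaves up to 49 later infusions. From the study days in the schedules: Week 49 is Day 337, so (337 − 1)/7 = 48 weeks after first dose. Week 197 is Day 1373, so (1373 − 1)/7 = 196 weeks.

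**3. What the planned tables can give about the acute change.**
- *Mean.* If the same participants contribute at both timepoints, mean(post) − mean(pre) equals the mean within-visit change exactly. This is recoverable.
- *Spread.* Var(post − pre) = Var(post) + Var(pre) − 2 Cov(post, pre). The tables give the two variances but not the covariance, so the SD of the change is not recoverable. Nor are its median, minimum and maximum.

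**4. What they can give about readings below 90 mm Hg.**
- A summarised reading below 90 forces the minimum at that timepoint below 90, so it is visible.
- The number of participants is not. If the minimum is below 90 and the median is at least 90, between 1 and n/2 participants are below: 1 to 20 for n = 40, 1 to 10 for n = 20, 1 to 3 for n = 6. Mean and SD may narrow this but do not fix it.
- The counts cannot be added over visits, because the tables do not identify people. A minimum below 90 at ten visits could be one participant or ten.
- The minimum does not show whether that participant was already below 90 before the infusion.

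**5. How little the mean shows.** The documents give no blood pressure values, so a fall of 30 to 50 mm Hg in one participant is an assumption. The shift in the mean is fall/n.

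| n | Fall 30 | Fall 50 |
|---|---|---|
| 40 (all participants) | 0.75 | 1.25 |
| 20 (cohort ceiling) | 1.5 | 2.5 |
| 6 (asymptomatic ceiling, from Study AL001-1) | 5.0 | 8.3 |

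In the larger groups, then, a single event would be seen in the minimum and hardly at all in the mean.

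**6. The readings left out.** Readings beyond 60 minutes in a running infusion arise when it has been interrupted or slowed. Protocol 5.1.2 prescribes halting the infusion and resuming at a reduced rate after a reaction. A low value in that window would reach the listing but not the minimum column. If the infusion is stopped for good, later readings count as after its end and are summarised.

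**The case against.** The strongest reply is that the plan does what it promises. The endpoint is change in vital signs from baseline over time, SAP 6.3 delivers that, and it agrees with Protocol 8.4.2.6. Neither document says why the readings are paired, so a reader who infers that they exist to detect infusion effects goes beyond the text. That stands: a same-day reference would be an addition, and its absence is not a deviation.

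A reader might also infer that only means are reported, or that a systolic value below 90 would appear in no vital-sign table. The documents do not support either. Minimum and maximum are part of the defined statistics, and post-infusion readings are all summarised.

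The event also has other routes. Protocol 6.5.7 sends clinically significant abnormalities to the adverse event form, and Protocol 7.3 adds findings that need treatment or discontinuation. These reach the TEAE tables, including those leading to study drug discontinuation (SAP 6.1.1, 6.1.5). SAP 5.3 summarises interrupted doses and lists the reasons. Moreover, the protocol event is *symptomatic* hypotension, and vital-sign data carry no symptoms. All this stands, and it is why the point is modest.

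These routes do not close the gap. The adverse event route depends on a judgement of clinical significance. Protocol 7.1 asks for the diagnosis in preference to symptoms, so a fall in pressure may be recorded under a reaction term, and SAP 6.1.1 plans no infusion-reaction summary. The listing could cover up to 40 × 50 = 2,000 infusions, which is hard to count by hand.

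A last objection bears on the remedy. Appendix 3 of the protocol schedules during-infusion readings (about 15 and 45 minutes) only for home infusions. Pooling them with post-infusion readings would give some participants more chances to fall below 90. That is right, and the fix separates them.

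**Conclusion.** The point holds as a limited one. SAP 6.3 measures change only from the pre-first-dose baseline and counts no vital-sign cut-off. From the vital-sign tables a reader can obtain the mean acute change (if the same participants contribute before and after) and the lowest value at each visit and timepoint. The reader cannot obtain the spread of the acute change, or the number of participants with a systolic value below the protocol's 90 mm Hg figure.

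This conclusion rests on the text of the two documents and on the identities in the working. Only the 30 to 50 mm Hg falls are assumed, and the conclusion does not depend on them. No estimate is offered of how much smaller the within-visit SD would be, because the documents give no SD or correlation. It does not follow that acute hypotension would go unreported, or that the plan departs from its endpoint. This is a better summary of data already collected, at small cost.

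**What to change.** In SAP 6.3:

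1. **Within-visit change.** Summarise scheduled end-of-infusion minus same-day pre-dose for blood pressure, pulse, temperature and respiratory rate, by visit. Keep change from the pre-first-dose baseline for the pre-dose values.
2. **Participant count.** Give n (%) of participants with at least one scheduled post-infusion systolic value below 90 mm Hg, and the number of those with a same-day pre-dose value of 90 or above. State the denominator. Label it a blood pressure count and not symptomatic hypotension, because symptoms come from the adverse event data.
3. **During-infusion readings.** Report these separately, including those taken more than 60 minutes after the start that are now left out of the summary. State that they are scheduled only for home infusions.

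While the section is open, correct two cross-references. Baseline is defined in SAP Section 2, not Section 4. The cited Protocol section 5.5.4 does not exist, and the interruption rules are in Protocol 5.1.2.

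The cost is SAP wording and a few extra tables, with no new assessments. The remaining drawback is uneven ascertainment of during-infusion readings, which separate reporting makes visible but does not remove. No clinical threshold or stopping rule is proposed; 90 mm Hg is the protocol's own figure.
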